4.2 Setting

HIV-positive subjects will be recruited from eight clinics: St. Mary's Hospital; King's College Hospital; Chelsea and Westminster Hospital; Homerton University Hospital; Mortimer Market Centre; Brighton and Sussex University Hospital; Royal Free Hospital; and the Mater Misericordiae University Hospital Dublin. The seven UK clinics participate in the UK CHIC Study, providing annual downloads of data (demographics, AIDS events, deaths, laboratory tests, antiretroviral use, viral hepatitis co-infections) on patients seen for care. These data undergo extensive cleaning prior to inclusion in the dataset. Linkage to the UK CHIC Study will allow capture of historic HIV data for these patients thus allowing for efficiencies in data collection. Similar data extracts will be conducted from the Dublin HIV Cohort Database.

4.2.1 Recruitment of HIV-positive cohorts

A list of individuals eligible for the older HIV-positive cohort will be generated at each clinic by study co-ordinators in collaboration with the lead consultant at the clinic, thus ensuring no unnecessary transfer of patient identifiable data out of the clinic. Patients will be randomly sampled from the list, with black African heterosexual men and women, and white heterosexuals (men or women) being over-sampled so that the final cohort includes 100 participants in each of these three groups. Clinic lists of younger patients attending each clinic will be stratified by age, gender, ethnicity and sexual orientation; eligible patients will then be sampled from these lists at a rate determined by the demographic profile of the older patients at the clinic.

Recruitment targets at each clinic are shown below in table 2:

Table 2: Recruitment targets at each site

Centre	Patients seen in 2008/09		Recruitment targets			Total
	<50 years	>50 years	HIV positive years	HIV negative years	>50 years	
St. Mary's Hospital	1406	317	60	120	60	240
King's College Hospital	1264	207	40	80	40	160
Chelsea & Westminster Hospital	3146	902	190	380	190	760
Homerton Hospital	445	73	15	30	15	60
Mortimer Market Centre	2246	468	90	180	90	360
Brighton and Sussex Hospital	1159	386	80	160	80	320
Mater Misericordiae University Hospital Dublin	536	65	25	50*	25	100
Total	10202	2418	500	1000	500	2000

*these subjects are already recruited into the Dublin HIV cohort study, therefore high rates of recruitment are considered feasible.

The recruitment target for Royal Free Hospital, open for recruitment as of November 2015, is as follows: 25 patients > 50 years HIV-positive; 13 patients < 50 years HIV-positive; and 13 HIV-negative controls (total of 51).

4.2.2 Recruitment of HIV-negative cohort

HIV-negative subjects will be recruited through HIV/genitourinary medicine clinics, the HIV/gay/African press, community organisations, internet sites and churches, by the study coordinator and steering committee members; several members of the steering committee have substantial experience of recruiting gay men and black African men/women to research studies from community sites, and have developed successful strategies to identify and recruit HIV-negative volunteers that match the demographic profile of our target groups.

4.3 Study Objectives

Clinical manifestations

- To describe the incidence and presenting features of serious medical conditions (such as cardiovascular, liver, renal disease, cancer and fragility fractures) in the three cohorts.
- To describe the outcomes of serious medical conditions (including time to recovery/resolution, where applicable, the incidence of complications and use of health-care).
- To compare NC function in the three cohorts, and to identify predictors of NC function.
- To compare the levels of musculoskeletal pain in the three cohorts, to identify predictors of this and to describe the health-care needs of those affected.
- Among women, to assess the effects of menopausal status on cardiovascular disease, BMD and lipid/glucose metabolism.

Antiretroviral pharmacokinetics and drug interactions

- To describe plasma (or, where appropriate, intracellular) concentrations of antiretroviral agents (tenofovir, non-nucleoside reverse transcriptase, protease, integrase and entry inhibitors) at baseline in the older HIV-positive cohort, and to compare these to those seen in younger HIV-positive patients.
- To describe the incidence of toxicities/drug discontinuations and immunological/virological responses to cART in the HIV-positive cohorts and to assess correlations between these events and plasma drug concentrations.
- To describe the level of poly-pharmacy in the older HIV-positive cohort and thus the potential for/prevalence of unwanted drug-drug interactions.
- To determine whether accumulation of renally-excreted antiretroviral drugs (e.g. tenofovir) increases their potential to cause renal injury in older HIV-positive people.

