3.5 Summary

Our study, by enrolling both younger and older HIV-positive individuals with a matched HIV-negative control group, will be in the unique position to determine the effects of ageing and HIV status on chronic HIV-infection. In addition, results from this study will be well placed to assist in informing future HIV treatment guidelines on the monitoring of chronic HIV infection in older subjects and assisting in the design of future interventional studies for the treatment of age associated co-morbidities.

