4.0 Study Plan

Aim:

1. To analyse the incidence and outcomes of co-morbidities in older-HIV-positive people and their relationship with demographic/clinical factors.
2. To evaluate associations between antiretroviral drug concentrations and age, and to assess the potential impact of age on drug efficacy, drug-drug interactions and co-morbidities.
3. To contribute to the development and implementation of evidence-based recommendations for the clinical monitoring of older HIV-positive patients.

Design:

Multicentre, prospective, observational study over 3 years

Our study will describe the impact of advancing age on the experience of living with HIV in England and Ireland. To address this we will establish cohorts of HIV-positive people aged >50 and <50 years as well as demographically matched HIV-negative people aged >50 years.

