4.1 Study population

Inclusion Criteria

Older HIV-positive cohort (n=1000):

- documented HIV infection
- age ≥ 50 years at study entry
- self defined white or black African ethnicity
- likely route of HIV acquisition via sexual exposure
 - Either by male to male exposure if white or by heterosexual exposure if white or black African
- able to comprehend study patient information leaflet

Subjects with primary HIV infection are eligible and investigators are encouraged to recruit such subjects.

Our target population (those of white or black African ethnicity and those infected with HIV via sexual routes) has been chosen as these groups represent the vast majority of older HIV-positive individuals attending for care in the UK; analyses of other groups (e.g. injection drug users, those infected through blood/blood products and transgender individuals), who may have very different needs and outcomes, would likely be under-powered.

Younger HIV-positive cohort (n=500):

- documented HIV infection
- age < 50 at study entry*
- self defined white or black African ethnicity
- likely route of HIV acquisition via sexual exposure
 - Either by male to male exposure if white or by heterosexual exposure if white or black African.
- able to comprehend study patient information leaflet

* this group will comprise of at least 150 subjects in each of the following age groups: 20-29, 30-39, 40-49 years. Recruitment will be monitored by the Study Monitoring Team

HIV-negative cohort (n=500):

- documented negative HIV test at screening
- age ≥ 50 years at study entry
- self defined white or black African ethnicity
- registered with a General Practitioner and gives permission for contact with that GP.

Exclusion Criteria

- in the opinion of the investigator, those unable or unwilling to comply with the requirements of the study
- life expectancy less than 6 months

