8.0 Statistical Considerations

8.1 Methods and planned analysis clinical manifestations

Detailed information on clinical events will be collected at baseline and at each visit. As we currently have very little data on the incidence, presenting features or outcomes of these events in older HIV-positive individuals, many of the analyses will be descriptive. We will describe the proportion of individuals in the three cohorts who have already experienced each event at baseline (prevalence) and the proportions who develop a new (or recurrent) event over follow-up (incidence). Confidence intervals will be generated for these proportions. Statistical comparisons of the prevalence/incidence of each event (where numbers are sufficiently large) will be performed using logistic/Poisson regression.

Sample size and power

The sample sizes for baseline analyses will be 1000, 500 and 500 respectively.

Based on data from Goulet *et al*⁵, we expect baseline prevalence rates of liver/renal disease of around 14.0%/4.6% among those aged >50 years versus 5%/1% in younger HIV-positive patients and 3.1%/2.3% in HIV-negative patients. Our study will have 70-100% power to detect similarly-sized differences between the three cohorts. Serious medical conditions are, however, expected to be rare, even in the older groups. For example, based on the limited data that exist (from various sources), we may see at most only 17, 20, and 7 cases of myocardial infarction, malignancy and liver failure, respectively, in the HIV-positive groups combined; analyses of incidence of these events will therefore be descriptive. Incident fractures and chronic kidney disease may be more common (105 and 100, respectively), but these numbers will still limit multivariable analyses. NC function impairment and current pain are expected to be present in 40% (n=540) and 63% (n=850) of the HIV-positive subjects at baseline; we will therefore have >95% power (5% significance level) to detect differences of 10% between the proportions with each event in the older HIV-positive and other cohorts; these sample sizes will also permit multivariable analyses of predictive factors. Among the older women (130 or so in the white/black African groups combined), we estimate that 70 (54%) will have already experienced the menopause at baseline; our analyses will be limited to simple comparisons of biomarkers in the two groups.

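### The three-cohort comparison names no contrasts, although HIV-negative people enter only at 50 or over and younger HIV-positive people only under 50, so one of its three pairs cannot separate HIV from age

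*Combined protocol and SAP*

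**What the plan says.** Section 4.1 defines three cohorts. The older HIV-positive cohort (1000) and the HIV-negative cohort (500) both require "age ≥ 50 years at study entry"; the younger HIV-positive cohort (500) requires "age < 50 at study entry". Section 4.0 describes the controls as "demographically matched HIV-negative people aged >50 years". No HIV-negative group under 50 is planned.

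Two objectives in 4.3 ask for a comparison across all three groups: "To compare NC function in the three cohorts, and to identify predictors of NC function" and "To compare the levels of musculoskeletal pain in the three cohorts". Section 8.1 adds that event prevalence and incidence will be compared by logistic or Poisson regression where numbers allow. It gives no reference cohort, list of contrasts or age term. Section 8.3 covers only the timing of analyses.

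On liver and renal disease, 8.1 states: "Our study will have 70-100% power to detect similarly-sized differences between the three cohorts". For neurocognitive impairment and pain it is narrower, giving more than 95% power for 10-point differences between the older HIV-positive cohort and the others. Section 3.5 says the study "will be in the unique position to determine the effects of ageing and HIV status on chronic HIV-infection".

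**The concern.** With two HIV states and two age bands there are four cells, and the eligibility criteria fill three. Two of the three possible pairs have a clear meaning. Older HIV-positive versus HIV-negative addresses HIV status at 50 or over. Older versus younger HIV-positive addresses ageing within HIV. The third pair, younger HIV-positive versus HIV-negative, differs in both factors at once.

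Because 4.3 and 8.1 leave the comparison unrestricted, that third pair falls within their wording. An analyst who reports all pairwise results could present an age difference as an HIV difference, or could miss an HIV difference that age has cancelled. The usual remedy, adjusting for age, is weak here. The two age ranges do not overlap at entry, so any separation rests on extrapolating an age effect and assuming it is the same with and without HIV.

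A related gap concerns ageing. Section 3.2 itself notes that glomerular filtration declines with age and that some cognitive decline is normal. The older-versus-younger HIV-positive contrast contains that normal ageing, and there is no HIV-negative group under 50 to measure it against.

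**Working it through.** **Inputs (8.1).** Sizes: older HIV-positive (O) 1000, younger HIV-positive (Y) 500, HIV-negative (N) 500. Expected liver disease: O 14.0%, Y 5%, N 3.1%. Expected renal disease: O 4.6%, Y 1%, N 2.3%. The 5% level is stated in 8.1 only for neurocognitive impairment and pain. I assume it also applies here, and that it is two-sided.

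**Formula.** Power = Φ[(|p1 − p2| − 1.96·SE0)/SE1]. SE0 uses the pooled proportion and SE1 the separate ones. The unpooled version replaces SE0 by SE1.

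**Worked example, renal O v N.** The pooled proportion is (46 + 11.5)/1500 = 0.0383. SE0 = √(0.0383 × 0.9617 × 0.003) = 0.01052. SE1 = √(0.046 × 0.954/1000 + 0.023 × 0.977/500) = 0.00942. Pooled: (0.023 − 1.96 × 0.01052)/0.00942 = 0.25, so power is 60.0%. Unpooled: 0.023/0.00942 − 1.96 = 0.48, so power is 68.5%.

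**Reproducing the stated 70-100%.**

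| Pair | Liver | Renal (pooled / unpooled) |
|---|---|---|
| O v Y | about 100% | 98.1% / 99.5% |
| O v N | about 100% | 60.0% / 68.5% |
| Y v N | 33% | 36.4% / 36.5% |

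The range is roughly recovered for pairs that contain the older HIV-positive cohort. Its lower end is generous: renal O v N passes 70% only with a one-sided test (72.7%, pooled). It is not recovered for Y v N. With a 10% shortfall (900/450/450), Y v N falls to about 30% (liver) and 33% (renal), and renal O v N to 55-64%.

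**Neurocognitive impairment and pain.** For a 10-point difference from 40% or 63%, 1000 v 500 gives 95.7-97.5%, which agrees with the stated figure of more than 95%. Y v N (500 v 500) gives 89.0-92.5%.

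**What the mixed pair measures.** Renal odds are 0.046/0.954 = 0.0482 (O), 0.01/0.99 = 0.0101 (Y) and 0.023/0.977 = 0.0235 (N).

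- O v N: 0.0482/0.0235 = 2.05
- O v Y: 0.0482/0.0101 = 4.77
- Y v N: 0.0101/0.0235 = 0.43, which is 2.05/4.77

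The third ratio is the HIV contrast divided by the age contrast, so it estimates neither. Liver odds are 0.1628, 0.0526 and 0.0320. They give O v N 5.09, O v Y 3.09 and Y v N 1.65 (= 5.09/3.09): attenuated, but in the same direction.

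**The case against.** The best defence is that the authors probably meant only the two sensible contrasts. The plan never names younger HIV-positive versus HIV-negative, nor an overall three-group test. The neurocognitive and pain power sentence is anchored on the older HIV-positive cohort, and the liver and renal range fits only pairs that include it. Section 8.1 also says many analyses will be descriptive, and describing three groups separately confounds nothing. This stands as evidence of intent. It does not remove the gap, because the objectives and the regression plan do not carry the restriction and the liver and renal power sentence is worded for all three cohorts.

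Three stronger readings are tempting but unsupported.

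- A reader might infer that the design reverses the HIV effect in general. The sign change appears only in the expected renal rates, about 5 versus 11.5 cases per 500. Liver disease does not reverse. Section 8.1 does not give the age of the people behind the 2.3%, so attributing the reversal to age is an assumption. No cohort-specific neurocognitive or pain rates are given, so nothing can be shown for those outcomes.
- A reader might infer that the plan claims to show accelerated ageing. Section 3.5 speaks of effects of ageing and HIV status on chronic HIV infection, and 4.0 of describing the impact of age on living with HIV. Neither says that ageing is worse with HIV.
- A reader might conclude that every three-group test must go. A three-level cohort term with the right reference delivers both useful contrasts, so banning it is a preference.

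**Conclusion.** The point holds as a fault of specification; the design has not failed. Two of the three contrasts are interpretable. The third cannot separate HIV from age, and the plan neither excludes it nor labels it. The stated 70-100% power is wrong for that pair (about 33% liver, 36% renal) and somewhat high for renal disease in older HIV-positive versus HIV-negative participants (about 60-68%). The odds ratios of 2.05 and 0.43 show how far the mixed pair can mislead, but only on the plan's expected renal rates. The power figures assume the planned cohort sizes, a two-sided 5% level, no multiplicity adjustment and a normal approximation. The lack of age overlap at entry follows from eligibility and needs no assumption. This is a cheap improvement worth making.

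**What to change.** - **8.1, contrasts.** Name the older HIV-positive cohort as the reference. Pre-specify two inferential contrasts: versus HIV-negative (HIV status at 50 or over) and versus younger HIV-positive (ageing within HIV, including normal ageing). Label younger HIV-positive versus HIV-negative as descriptive and confounded by age. A three-level cohort model may stay.
- **8.1, power.** Restate the liver and renal claim for the two named contrasts, giving the test and sidedness, with renal disease versus HIV-negative at about 60-68% under the assumptions above.
- **4.3.** Refer the neurocognitive and pain objectives to these contrasts.
- **Exploratory analysis.** Add an age-by-HIV interaction among the roughly 1500 participants aged 50 or over (1000 + 500), where both HIV states are present, to ask whether age associations differ by HIV status.
- **3.5.** Say that the older-versus-younger contrast alone cannot answer that question.

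The cost is a few sentences and one model term, with no new participants or measurements. The stated claim becomes narrower, and the interaction will have wide intervals for rare events.

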5.0 Study visits

5.1 Screening

Each subject must sign an Informed Consent Form prior to the conduct of any screening procedures.

The purpose of the screening visit is to evaluate that the subject meets study inclusion/exclusion criteria. HIV antibody testing will be undertaken for subjects undergoing screening for the HIV-negative cohort.

5.2 Visit 1 (Baseline visit)

The baseline visit will perform evaluations as per schedule of visits (2.0).

The baseline visit is expected to take 1-2 hours; if possible the subject should attend fasted. The following information will be collected:

- Baseline demographics: age; sex; ethnic group; sexual orientation; country of birth; education.
- Socio-economic status: immigration status; employment; household dependents; household income; housing.
- Quality of life questionnaire.

- Anthropometrics: height; weight; body mass index; waist circumference.
- Lifestyle factors: current/past cigarette smoking; alcohol use; recreational drug use.
- Full clinical history: to include cardiovascular events (hypertension, myocardial infarction, angina or acute coronary syndromes, cardiogenic arrhythmias, coronary artery stenting/bypass grafting, peripheral vascular disease), renal failure, liver failure, diabetes, malignancies, falls, fractures, joint disease or joint replacements.
- Measurement of hand grip strength using an automated device.
- Simple measurement of walking speed over a distance of 15 feet (457 cms).
- Blood pressure will be estimated using an automated device.
- Menstrual and reproductive history (women), including menopausal status
- Family medical history: to include any cardiovascular disease, type 2 diabetes mellitus, malignancies, mental illness, dementia or Alzheimer's disease, parental hip fractures.
- Current and recent (over past 12 months) antiretroviral use: type of antiretroviral; start/stop dates; dose; frequency of dosing; side effects; reasons for prior changes/discontinuations.
- Duration of HIV infection and date of HIV-seroconversion if known
- Adherence assessment (see study questionnaire in appendix 1)
- Use of any other medications (including, but not limited to, anti-hypertensives, anti-depressants, vitamin D and/or calcium replacement therapy, lipid-lowering drugs, regular use of analgesics, herbal remedies, other over-the-counter drugs): type of drug; start/stop dates; dose; frequency of dosing; side effects.
- Neurocognitive function: specific memory and cognitive testing assessing cortical and sub-cortical function.
- Pain assessment: regional and widespread pain collected using a validated mannequin; nature of onset; duration; intensity; resulting disability (see study questionnaire in appendix 1)
- DXA scan for bone mineral density (full body DXA where available). These should be performed within 30 days of the clinic appointment.
- Falls risk (see study questionnaire in appendix 1)
- Fracture risk (see study questionnaire in appendix 1)
- Frailty assessment (see study questionnaire in appendix 1)
- Most recent laboratory tests will be recorded (assessed in the HIV-negative cohort): renal, liver, lipid and bone profiles, glucose, full blood count, sexual health screen, hepatitis C serology. These tests should have been performed within a year of the clinic visit.
- Blood (serum, plasma, and PBMC) and urine samples: stored for subsequent projects of the potential pathogenic mechanisms underlying age-related diseases. This will include assessment of vitamin-D and PTH
- Blood (plasma) will be collected for pharmacokinetic analysis (including but not limited to antiretroviral drug exposure)

5.3 Visit 2 (1st year follow up visit)

This follow up visit will be performed as per schedule of visits (2.0).

Only HIV-positive cohorts will be invited to undertake this visit with this visit expected to take 1 hour.

The following will be assessed:

- Changes to lifestyle and socio-economic status over the past year.
- Significant clinical events occurring over the past year: dates of onset and resolution, use of medical services, changes to antiretroviral and other medications, and resulting ongoing health concerns.
- Blood pressure will be estimated using an automated device.
- Details of access to health care services over the past year: visits to the general practitioner, hospital, counselors, psychiatrists, psychologists and medical investigations performed (information obtained by direct questioning and through HIV note review). Permission will be sought to contact the patient's general practitioner and/or hospital for further details.

- Most recent laboratory tests will be recorded: renal, liver, lipid and bone profiles, glucose, full blood count, sexual health screen, hepatitis C serology (Within the past year)
- Concomitant medications: start/stop dates; dose; dosing frequency; side effects.
- Fracture occurrence and fracture risk (see study questionnaire in appendix 1)
- Regional and widespread pain.

5.3a Visit 2 (1st year follow up visit) for HIV negative participants.

These participants will be contacted by telephone by arrangement with the study nurse. They may be asked to attend the clinic in order to facilitate this visit.

Details of any changes in circumstances or illnesses and medication will be documented.

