2.0 Schedule of Visits

Study Visit	Screening	Baseline	Follow up visits	
	Within 60 days of baseline	Visit 1	Visit 2 (12 months after visit 1) HIV positive cohorts only	Visit 3 (24 months after visit 1)
Informed Consent	x			
Review Eligibility	x	x		
Detailed medical history as per protocol		x	x	x
Study Questionnaire		x	x	x
Respiratory questionnaire				x
Neurocognitive assessment		x		x
DXA scan			x	
Blood sampling		x		x
Phone contact			x (HIV negative cohort)	x

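### Only HIV-positive participants are measured at year 1, so the HIV-positive v HIV-negative incidence ratio for CKD can be inflated to the extent that cases come from study measurements

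*Combined protocol and SAP*

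**What the plan says.** Protocol 5.3 restricts the year-1 clinic visit: "Only HIV-positive cohorts will be invited to undertake this visit with this visit expected to take 1 hour". The schedule in 2.0 agrees: "Visit 2 (12 months after visit 1) HIV positive cohorts only". At that visit, "Blood pressure will be estimated using an automated device" and "Most recent laboratory tests will be recorded: renal, liver, lipid and bone profiles, glucose, full blood count".

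For the HIV-negative cohort, 5.3a says: "These participants will be contacted by telephone by arrangement with the study nurse". The call covers changes in circumstances, illness and medication. Participants may be asked to come in for it, but no blood pressure or blood test is attached.

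At Visit 3 (5.4) every cohort has blood pressure and laboratory results. The laboratory values come from routine records of the previous year in HIV-positive people and are study-assessed in HIV-negative people.

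Section 4.2 adds a source for HIV-positive people only. The UK clinics take part in UK CHIC, "providing annual downloads of data (demographics, AIDS events, deaths, laboratory tests, antiretroviral use, viral hepatitis co-infections"; similar extracts are planned from the Dublin database.

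Section 8.1 counts as incident any new or recurrent event during follow-up, in each of the three cohorts. It continues: "Statistical comparisons of the prevalence/incidence of each event (where numbers are sufficiently large) will be performed using logistic/Poisson regression". Among incident outcomes it singles out two: "Incident fractures and chronic kidney disease may be more common (105 and 100, respectively". It gives no definition of CKD, no restriction to occasions shared by the cohorts and no allowance for the number of measurements.

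**The concern.** CKD is usually silent and comes to light through a test. If incident cases are read from study measurements, a group tested twice has more chances to cross a threshold than a group tested once. Extra error-prone readings can add cases but cannot remove them, so under no true difference the bias runs towards more disease in HIV-positive people. A fuller telephone script would not close the gap, because a call can capture a diagnosed illness but not an unnoticed abnormal value.

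This matters because 4.3 makes the incidence of renal disease in the three cohorts an objective, 3.5 relies on the HIV-negative controls to separate the effect of HIV from that of age, and CKD is one of only two incident outcomes that 8.1 expects to be relatively common.

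**Working it through.** **1. Scheduled follow-up occasions.** HIV-positive: Visits 2 and 3, so two. HIV-negative: Visit 3 only, so one. Older and younger HIV-positive participants have the same two.

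**2. The plan's own figure.** The 100 incident CKD cases, apparently for the HIV-positive cohorts combined, cannot be rebuilt: 8.1 gives no rate, definition or person-time. The denominator implied by other figures in 8.1 is 540/0.40 = 1350, so 100/1350 = 7.4% over follow-up (100/1500 = 6.7% on the full target).

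**3. Effect of persistence.** Take identical true disease, p = 7.4% found over two occasions, and let f be the share of those cases that are positive at Visit 3 (assumed). One occasion finds q = f × p, so the apparent ratio is 1/f. With d = p − q, 1000 v 500 people and a two-sided 5% test, the chance of false significance is Φ((d − 1.96·SE0)/SE1) + Φ((−d − 1.96·SE0)/SE1), where SE0 is pooled and SE1 unpooled.

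For f = 0.8: q = 5.93%, d = 0.0148, pooled share = (1000 × 0.0741 + 500 × 0.0593)/1500 = 0.0691, SE0 = √(0.0691 × 0.9309 × (1/1000 + 1/500)) = 0.0139, SE1 = 0.0134. The result is 18%.

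| f | HIV-negative share | Ratio | False significance |
|---|---|---|---|
| 1.0 | 7.4% | 1.00 | 5% |
| 0.9 | 6.7% | 1.11 | 8% |
| 0.8 | 5.9% | 1.25 | 18% |
| 0.7 | 5.2% | 1.43 | 36% |

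**4. Simulation of a single-value rule.** Each person has a true eGFR plus independent within-person error; a case is any follow-up value below 60 after 60 or more at baseline. Both groups have the same true values. Every input in the first column is an assumption. The test uses 1000 v 500, less those below 60 at baseline.

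| Mean, between-person SD; within-person SD; loss per year | One occasion | Two occasions | Ratio | False significance |
|---|---|---|---|---|
| 88, 16; 3; 4 | 7.0% | 7.4% | 1.05 | 6% |
| 88, 16; 3; 2 | 3.2% | 3.7% | 1.18 | 8% |
| 88, 16; 5; 2 | 3.9% | 5.1% | 1.30 | 16% |
| 88, 16; 8; 1 | 4.2% | 6.4% | 1.53 | 39% |
| 85, 15; 6; 0.5 | 3.2% | 5.0% | 1.56 | 33% |
| 80, 15; 6; 0.5 | 5.2% | 8.0% | 1.53 | 46% |

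Across means of 80 to 90 with within-person SD 6 to 8 and loss of 0.5 per year, the ratio stays at about 1.5-1.6. False significance moves with the event rate, from 21% (mean 90, SD 6) to 64% (mean 80, SD 8). In those noisy settings only about 31-42% of year-1 cases are still below 60 at year 2, so most extra cases are measurement error.

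The same exercise for systolic pressure (threshold 140, mean 128, between-person SD 13-15, within-person SD 6-12, all assumed) gives ratios of 1.42 to 1.62. It applies only if hypertension is analysed as an incident outcome.

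**5. After the change.** With the same occasions and the same rule in both groups, f plays no part: the expected ratio under no difference is 1.0 and the false-positive rate 5%, apart from the limits given under the fix.

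**The case against.** The documents do not say that incident cases come from applying a threshold to study values. Section 8.1 speaks of clinical events, and Visits 2 and 3 collect significant events with dates and use of services, which can be read as diagnosed conditions. On that reading the simulation does not describe the analysis. This stands, and the point is conditional for that reason; but 8.1 does not exclude the measured route, and more testing can also lead to more diagnoses.

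Chronic disease should persist to Visit 3. This also stands: full persistence and no loss remove the inflation of cumulative incidence. No definition in the plan secures that.

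A reader might infer three stronger things.

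- **Linked results give HIV-positive people four or more follow-up values against one.** The protocol records the most recent result at each visit and describes linkage as a means of capturing historic data. It does not say that linked values will define incident cases.
- **If CKD needs two abnormal values, HIV-negative cases must be zero.** That holds only if scheduled study tests are the sole source. HIV-negative entrants must permit contact with their general practitioner (4.1), 5.3a records illnesses and medication, and 5.4 asks about investigations elsewhere. No systematic record extraction is described, but a diagnosed case can be captured.
- **Hypertension, glucose and lipid abnormality are planned incidence outcomes.** They are not named as such in 4.3 or 8.1. Hypertension appears in the clinical history list of 5.2.

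**Conclusion.** The asymmetry is explicit in 5.3 and 5.3a, and 8.1 as written would count year-1 detections. The HIV-positive v HIV-negative incidence ratio for CKD can therefore be inflated with no true difference, to the extent that cases are identified from study measurements. The documents do not show that it is inflated, nor by how much.

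Under stated assumptions the ratio is 1.0 with full persistence and no loss, about 1.05-1.2 with small error and faster decline (6-8% false significance), and up to about 1.5-1.6 with noisy single values (mostly about 30-45%, wider at the extremes). The older v younger HIV-positive comparison is not affected, since both attend Visit 2. The change should be made: it is cheap and protects a contrast the study relies on.

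**What to change.** In 8.1, for HIV-positive v HIV-negative incidence of measurement-defined conditions:

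- State one case definition for all cohorts and apply it to the occasions they share, Visits 1 and 3.
- Count a recorded new diagnosis or new treatment alike in both groups, so that someone found at Visit 2 and treated is not missed because the Visit 3 value is normal.
- Use Visit 2 and linked routine values only for comparisons within the HIV-positive cohorts.
- Report a sensitivity analysis that shows the effect of including year-1-only and linkage-only detections.
- State the remaining limitation: Visit 3 laboratory values are routine results from the previous year in HIV-positive people and study-assessed in HIV-negative people. Diagnoses prompted by the extra testing can also still enter.

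The cost is analysis wording, with no new visits or tests. Fewer HIV-positive cases will count in this contrast, and a single-occasion definition is less specific for a chronic disease.
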